### 10.2 Packaging and Labeling

Vertex will supply the granules in stick packs in kits and LUM 100-mg/IVA 125-mg tablets in child-resistant weekly blister cards. Study drug labeling will be in compliance with applicable local and national regulations. Additional details regarding packaging, labeling, and dispensing for study drug will be included in the Pharmacy Manual.

### 10.3 Study Drug Supply, Storage, and Handling

Packaging and storage conditions for study drug are described in Table 10-1. The investigator, or an authorized designee (e.g., a licensed pharmacist), will ensure that all investigational product is stored in a secured area, under recommended storage conditions, and in accordance with applicable regulatory requirements. To ensure adequate records, all study drugs will be accounted for as described in Section 10.4.

**Table 10-1 Study Drug**

Drug Name	Formulation/ Route	Packaging (Formulation Strength)	Storage Condition
LUM/IVA	Granules/ Oral	Supplied as 100-mg LUM/125-mg IVA granules in 1 stick pack	Store at $\leq 25^{\circ}\text{C}$ (77°F) with excursions to $30^{\circ}\text{C}$ (86°F)
LUM/IVA	Granules/ Oral	Supplied as 150-mg LUM/188-mg IVA granules in 1 stick pack	Store at $\leq 25^{\circ}\text{C}$ (77°F) with excursions to $30^{\circ}\text{C}$ (86°F)
LUM/IVA matching placebo	Granules/ Oral	Supplied as and 0-mg LUM/0-mg IVA granules in 1 stick pack	Store at $\leq 25^{\circ}\text{C}$ (77°F) with excursions to $30^{\circ}\text{C}$ (86°F)
LUM/IVA	Fixed-dose tablet/ Oral	Supplied as 100-mg LUM/125-mg IVA tablets	Store at $\leq 25^{\circ}\text{C}$ (77°F) with excursions to $30^{\circ}\text{C}$ (86°F)

IVA: ivacaftor; LUM: lumacaftor

### 10.4 Drug Accountability

The pharmacist or designated study site staff will maintain information regarding the dates and amounts of (1) study drug received; (2) study drug dispensed to the subjects; and (3) study drug returned by the subjects/caregivers. Subjects/caregivers will be instructed to return all used and unused materials associated with the study drug to the site. These materials will be retained at the site according to instructions provided by Vertex or its designee until inventoried by the study monitor. The study monitor will review study drug records and inventory throughout the study.

## 10.5 Disposal, Return, or Retention of Unused Drug

The study site staff or pharmacy personnel will retain all materials returned by the subjects/caregivers until the study monitor has performed drug accountability. At the end of the study, the study monitor will provide instructions as to the disposition of any unused investigational product. If the study monitor authorizes destruction at the study site, the investigator will ensure that the materials are destroyed in compliance with applicable environmental regulations, institutional policy, and any special instructions provided by Vertex. Destruction will be adequately documented.

## 10.6 Compliance

To ensure treatment compliance, the investigator or designee will supervise all study drug dosing that occurs at the site. At each visit, site personnel will review that the subject is compliant with study drug dosing and remind the subject/caregiver of study drug dosing requirements. Compliance will also be assessed by ongoing study drug count.

If a subject/caregiver demonstrates continued noncompliance of study drug dosing despite educational efforts, the investigator should contact the medical monitor to discuss discontinuation of the subject from the study treatment while remaining in the study.

## 10.7 Blinding and Unblinding

### 10.7.1 Blinding

Part 1 is a double-blind study. The subjects/caregivers and all site personnel, including the investigator and the study monitor, and the Vertex study team will remain blinded to treatment assignments until database lock for Part 1 (i.e., database lock for data up to and including the Week 48 Visit) with the following exceptions:

- Any site personnel for whom this information is important to ensure the safety of the subject in the event of a life-threatening medical emergency
- Vertex Global Patient Safety (GPS) and Regulatory Affairs personnel to satisfy serious adverse event (SAE) processing and reporting regulations
- Unblinded statistician preparing the final (production) randomization list, who is not part of the study team
- Vertex Clinical Operations IWRS management
- Vertex Clinical Supply Chain
- Vertex medical monitor may, for matters relating to safety concerns, unblind individual subjects at any time
- Subjects and their parent/caregiver should not be informed of their study-related LCI, [REDACTED], and imaging results during Part 1 and Part 2 of the study regardless if the subject has prematurely discontinued treatment.

### Imaging Data Blinding

Despite treatment blinding, knowledge of the imaging data has the potential to suggest whether a subject has been administered active study drug or matching placebo. Therefore, during the conduct of Part 1 (i.e., up to and including the Week 48 Visit), the Vertex study team will have

no access to the postdose imaging data. The central reader of these data will only send the blinded files (no treatment group, with real values for baseline, but with dummy values for all the assessments after baseline) to Vertex to be used for developing the statistical programs.

### LCI Data Blinding

Despite treatment blinding, knowledge of the LCI results has the potential to suggest whether a subject has been administered active study drug or matching placebo. Therefore, during the conduct of Part 1 (i.e., up to and including the Week 48 Visit), the Vertex study team will have no access to the post first-dose LCI data. The central reader of these data will only send the blinded files (no treatment group, with real values for screening and baseline for LCI, but with dummy data for LCI for all the assessment values after baseline) to Vertex to be used for developing the statistical programs.

## **10.7.2 Unblinding**

At the initiation of the study, the study site will be instructed on the method for breaking the blind. The unblinding method will be either a manual or electronic process.

Unblinding of the individual subject's treatment by the investigator will be limited to medical emergencies or urgent clinical situations in which knowledge of the subject's study treatment is necessary for clinical management. In such cases, investigators will use their best judgment as to whether to unblind without first attempting to contact the medical monitor to discuss and agree to the need for unblinding. If investigators deem it not necessary to unblind immediately, they will first attempt to contact the medical monitor to discuss and agree to the need for unblinding. If investigators have tried but are unable to reach the medical monitor, they will use their best judgment, based on the nature and urgency of the clinical situation, and may proceed with unblinding without having successfully reached and discussed the situation with the medical monitor. In case of emergency, the investigator will have the final decision and unilateral right for unblinding.

Contact information for the medical monitor (or appropriate backup) will be provided in a separate document.

In addition, the Vertex Medical Information Call Center ( [REDACTED] ) will answer calls 24 hours a day, 7 days a week, 365 days of the year, and will triage these calls to the study medical monitor or appropriate backup.

If a subject's treatment assignment has been unblinded for a medical emergency or urgent clinical situation, the medical monitor will be notified within 24 hours of the unblinding event. The reason and the date of the unblinding will be documented clearly in the subject's study file. Information about the treatment assignment obtained from the unblinding will be maintained in a secure location with controlled access and will not be shared with the sponsor (Vertex), CRO, or any site personnel (other than the physician treating the subject). In addition, the investigator will consider whether the clinical event that prompted unblinding will be considered an SAE, according to the regulatory definitions or criteria for SAEs, and if so, submit an SAE report to Vertex GPS or designee, per Section 13.1.2.

Vertex GPS or designee will also unblind any SAE reports in compliance with regulatory reporting requirements. In addition, Vertex may, for matters relating to safety concerns, unblind individual subjects at any time.

## **11 ASSESSMENTS**

### **11.1 Timing of Assessments**

The schedule of assessments is shown in [Table 3-1](#) and [Table 3-2](#).

The following assessments must be performed in the order specified below when more than 1 assessment is required at a particular time point:

1. Vital signs should be performed before any other procedures that may affect heart rate (e.g., blood draws).

3. The MRI assessment may be performed up to 7 days before the scheduled visit. If the MRI assessment is performed before the scheduled visit, blood draws for serum chemistry, hematology, [REDACTED] may be performed on the day of the MRI assessment. Blood draws for any assessment performed on the same day as MRI testing must be collected before administration of any medications related to MRI procedures. [REDACTED]

- The MRI at Weeks 48 and/or 96 may be delayed for up to 60 days if the subject is recovering from a PEx. The last dose of the antibiotic regimen for the treatment of pulmonary infection or exacerbation must be completed at least 28 days before the MRI. If the 28-day antibiotic-free period is not completed before the 60-day extension ends, the MRI should be completed within 1 week of the end of the 60-day extension. If the MRI at Weeks 48 and/or 96 is delayed, all other assessments must also be delayed.

### **11.2 Subject and Disease Characteristics**

Subject and disease characteristics include the following: demographics, medical history, stature, and weight.

Medical history will be elicited from each subject's caregiver during screening. Based on the medical history, the subject will be assessed for any disqualifying medical conditions as

specified in the inclusion and exclusion criteria. The medical history should include a complete review of systems, past medical and surgical histories, and any known allergies.

### **11.3 Pharmacokinetics**

Not applicable.

### **11.4 Efficacy**

#### **11.4.1 MRI With Perfusion**

The proposed morpho-functional MR-scoring-system is reproducible and applicable for semi-quantitative evaluation of a large spectrum of CF lung disease severity. Data from a study conducted by the DZL network show that MRI detected abnormalities in lung structure and perfusion, and response to therapy for exacerbations in infants and preschool children with CF. These results support the development of MRI for non-invasive monitoring and as an endpoint in interventional trials for early CF lung disease. This scoring-system is being used routinely in the assessment of CF lung disease and as an endpoint for clinical trials by the DZL network and other CF Centers in Europe.

Children will be sedated according to the established sedation procedure used for diagnostic procedures at each site, such as oral or rectal chloral hydrate (100 mg/kg body weight, maximum dose of 2 g) ( $\pm$  phenobarbital) or propofol, and monitored during the MRI examination by MR-compatible pulse oximetry.

Detailed procedures for the assessment will be provided in the Imaging Manual.

#### **11.4.2 Multiple-breath Washout**

##### Screening Period

Subjects must complete the MBW assessment during the Screening Period. If a subject cannot perform the MBW assessment at the Screening Visit, this assessment may be repeated during the Screening Period (without repeating the other assessments required during the Rescreening Visit). The subject will be considered a screen failure if the MBW assessment cannot be performed (i.e., if 2 technically acceptable tests are not achieved) during the Screening Visit or during re-testing. During the Screening Period, the MBW test may be performed pre- or post-bronchodilator.

[figure not shown]

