- i The MBW assessment may be performed pre- or post-bronchodilator. The assessment will be performed in multiple replicates as described in the MBW manual. If the subject cannot perform the MBW assessment at the Screening Visit, this assessment may be repeated during the Screening Period. The subject will be considered a screen failure if the MBW assessment cannot be performed (i.e., if 2 technically acceptable MBW tests are not achieved) at the Screening Visit or during re-testing. Refer to Section 11.4.2 for details.

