**Table 3-2 Study VX16-809-121: Treatment Period and Safety Follow-up Visit**

Event/Assessment a	Treatment Period									ETT Visit b	Safety Follow-up Visit c
	Part 1: Placebo-controlled Period				Part 1/ Part 2 d	Part 2: Open-label Period e					
	Day 1	Day 3 (± 1 Day)	Day 15 (± 3 Days)	Weeks 12, 24, 36 (± 7 Days)	Week 48 (± 7 Days)	Day 338 f (± 1 Day)	Day 350 (± 3 Days)	Weeks 60, 72, 84 (± 7 Days)	Week 96 (± 7 Days)		
Abbreviated PE	X p				X p						
Serum chemistry q,r	X		X	X	X		X	X	X	X	X
Hematology q,r				X	X			X	X	X	X
MBW v	X			X	X			X	X	X	X
MRI	X w				X w,x				X w,w	X	

p An abbreviated PE will be performed 4 hours (± 30 minutes) postdose on Day 1 and at Week 48 (Section 11.5.4).

q Refer to Section 11.5.2 for details.

r If the MRI occurs before the scheduled study visit, this assessment may occur on the same day as the MRI assessment. Blood draws performed on the same day as the MRI assessment must be collected before administration of any medications related to MRI procedures.

v The MBW assessment should be performed pre-bronchodilator and before dosing. The assessment will be performed in multiple replicates. Refer to Section 11.4.2 for details.

w Subjects may complete the imaging assessment up to 7 days before the scheduled visit. Screening assessments must be completed, inclusion and exclusion criteria must be reviewed, and subjects must meet eligibility criteria relevant at the time before participating in the baseline MRI assessment up to 7 days before Day 1. If the MRI is performed before the scheduled visit, the blood draws for serum chemistry, hematology, and ██████████ may be performed on the day of the MRI assessment. Blood draws for any assessment performed on the same day as MRI testing must be collected before administration of any medications related to MRI procedures. ██████████

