##### Treatment Period

At all visits after the Screening Period, MBW tests should be performed pre-bronchodilator. Each MBW will be performed in multiple replicates at each visit according to the MBW manual.

LCI will be derived from MBW testing. LCI2.5 represents the number of lung turnovers required to reduce the end tidal inert gas concentration to 1/40th of its starting value, [REDACTED]

[figure not shown]
The mean LCI value at each visit will be calculated using all technically acceptable replicates. All LCI replicate values will be provided by a central reader; however, the LCI central reader will not perform the calculation for the mean LCI values at visits. The mean LCI value at each Treatment Period Visit will be calculated by the sponsor or sponsor designee from the technically acceptable values provided by the LCI central reader.

[figure not shown]
Detailed MBW procedures will be supplied in the Study Reference Manual.

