### 12.3.1 General Considerations

All individual subject data for all randomized subjects exposed to study drug will be presented in data listings.

**Continuous variables** will be summarized using the following descriptive summary statistics: the number of subjects (n), mean, SD, median, minimum value, and maximum value. The precision of the measurement for each continuous variable will be specified in the SAP.

**Categorical variables** will be summarized using counts and percentages. Percentages will be presented to 1 decimal place.

**Baseline value**, unless otherwise specified, will be defined as the most recent non-missing measurement (scheduled or unscheduled) collected before the initial administration of study drug. [REDACTED]

**Change (absolute change) from baseline** will be calculated as post-baseline value - baseline value. [REDACTED]

**Relative change from baseline** will be calculated as (post-baseline value - baseline value)/baseline value. [REDACTED]

**The Treatment-emergent (TE) Period** will include the time from the first dose to the Safety Follow-up Visit or 14 days after the last dose of the study drug for subjects who do not have a Safety Follow-up Visit. [REDACTED]

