9 STATISTICAL ANALYSIS

9.1 General Considerations

As summarized in Table 7-1, the 2 treatment groups in Part 1 are

- LUM/IVA
- Placebo (PBO)

and the 2 treatment sequences from Part 1 to Part 2 are as follows:

- LUM/IVA → LUM/IVA
- PBO → LUM/IVA

Continuous variables will be summarized using the following descriptive summary statistics: the number of subjects (n), mean, SD, median, minimum value (min), and maximum value (max).

Categorical variables will be summarized using counts and percentages.

Unless otherwise specified,

- the **Study Baseline** value is defined as the most recent non-missing measurement (scheduled or unscheduled) collected before the first dose of study drug (including the matched placebo). The study baseline will be used to calculate the absolute and relative change from baseline for efficacy analyses, unless otherwise specified.
- the **LUM/IVA Baseline** value is defined as the most recent non-missing measurement (scheduled or unscheduled) collected before the first dose of study drug of Part 1 if the subject actually received at least one dose of LUM/IVA in Part 1, or before the first dose of study drug of Part 2 if the subject did not actually receive at least one dose of LUM/IVA in Part 1. The LUM/IVA baseline will be used to calculate the change from baseline in safety analysis in the FA, unless otherwise specified.

Absolute change from baseline will be calculated as post-baseline value – baseline value.

Relative change from baseline will be calculated as (post-baseline value – baseline value)/baseline value.

Unscheduled visits: Unscheduled visit measurements will be included in analysis as follows:

- 1) In scheduled visit windows per specified visit windowing rules
- 2) In the derivation of baseline and last on-treatment measurements
- 3) In the derivation of maximum and minimum values, and maximum and minimum change from baseline values during analysis period for safety analyses
- 4) In individual subject data listings as appropriate

Visit windowing rules: The analysis visit windows for protocol-defined visits are provided in [Appendix A](#).

Incomplete/missing data will not be imputed, unless specified otherwise.

Outliers: No formal statistical analyses will be performed to detect or remedy the presence of statistical outliers, unless specified otherwise.

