9.2.2.2.2 Analysis Method

Both within-treatment arm change and between treatment arm difference will be analyzed for secondary variables, subject to the considerations described below.

Absolute change from baseline in LCI_{2.5} through Week 48:

Analysis of within-treatment arm change will be based on descriptive summary statistics. The change from baseline to the average of all post-baseline measures at scheduled visits through Week 48 (defined as the average of Week 12, 24, 36, 48) will be used for this analysis.

Descriptive summary statistics include number of subjects (n), mean, median, SD, minimum, and maximum, along with the corresponding 95% CIs will be provided.

If the LUM/IVA treatment group or the placebo group demonstrates a within-treatment arm change with 95% CI excluding 0, and the variability of this variable is within expectation, the analysis of between-treatment difference may also be performed based on the descriptive summary statistics with the corresponding 95% CIs.

In addition, the summary of raw values and the absolute change from baseline at each post-baseline visit up to Week 48 will be provided.

Absolute change in Weight z-score from baseline at Week 48:

[figure not shown]
Absolute change in Stature z-score from baseline at Week 48:

[figure not shown]
Absolute change in BMI z-score from baseline at Week 48:

Analyses of within-treatment arm change will be based on descriptive summary statistics. The change from baseline at Week 48 will be used for this analysis. Descriptive summary statistics including number of subjects (n), mean, median, SD, minimum, and maximum, along with the corresponding 95% CIs will be provided.

If the LUM/IVA treatment group or the placebo group demonstrates a within-treatment arm change with 95% CI excluding 0, and the variability of this variable is within expectation, the analysis of between-treatment difference may also be performed based on the descriptive summary statistics with the corresponding 95% CIs.

Additional summary of raw values and absolute changes from baseline at each post-baseline visit up to Week 48 will also be provided.

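### A child with no usable Day 1 washout test can get a post-bronchodilator screening value as LCI2.5 baseline, while all later tests are to be pre-bronchodilator

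*Protocol*

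**What the plan says.** **Test condition.** At screening, Protocol 11.4.2 states "During the Screening Period, the MBW test may be performed pre- or post-bronchodilator", and footnote i of Table 3-1 repeats this: "The MBW assessment may be performed pre- or post-bronchodilator". After screening, Protocol 11.4.2 states "At all visits after the Screening Period, MBW tests should be performed pre-bronchodilator". Footnote v of Table 3-2, whose MBW row includes Day 1, states "The MBW assessment should be performed pre-bronchodilator and before dosing".

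**Baseline.** Under Protocol 12.3.1 the baseline, unless otherwise specified, "will be defined as the most recent non-missing measurement (scheduled or unscheduled) collected before the initial administration of study drug". SAP 9.1 uses the same rule for the Study Baseline: the "value is defined as the most recent non-missing measurement (scheduled or unscheduled) collected before the first dose of study drug". In SAP Appendix A, Table 12-1, the MBW baseline window is any pre-dose value up to study day 1. Neither rule mentions bronchodilator status.

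**Endpoint.** LCI2.5 change through Week 48 is a secondary endpoint: the average of Weeks 12, 24, 36 and 48 minus the single baseline (SAP 9.2.2.2.2). The SAP allows the between-arm comparison if either arm "demonstrates a within-treatment arm change with 95% CI excluding 0" and the variability is as expected.

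**The concern.** The protocol holds the bronchodilator condition fixed at every scheduled visit except screening, and the baseline rule does not carry that restriction over. A screening value is available as a fallback for essentially every randomized child, because two technically acceptable tests are needed to enter the study. No visible text requires an acceptable Day 1 test before dosing. At ages 2 to 5 some Day 1 tests may fail; the protocol itself provides for repeat testing at screening when a child cannot perform MBW.

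For a child who falls back to a post-bronchodilator value, any bronchodilator effect on LCI2.5 enters the change score in full. Averaging four follow-up visits does not dilute it, because the error sits in the one baseline value that is subtracted. The within-arm mean change moves accordingly, and the SAP uses that quantity when deciding whether the between-arm LCI comparison may be made.

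**Working it through.** The plan states no figure on this point. The check is a trace of the rules, followed by an illustration on assumed inputs.

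**Trace of the baseline rule**

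| Day 1 MBW | Screening MBW | Baseline selected | Same condition as follow-up? |
|---|---|---|---|
| Usable | Either | Day 1, pre-bronchodilator | Yes |
| Not usable | Pre-bronchodilator | Screening | Yes |
| Not usable | Post-bronchodilator | Screening | **No** |

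Only the last row is a problem. The table takes Day 1 and follow-up tests as performed to plan.

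**Size**

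Let d be a child's pre-bronchodilator LCI2.5 minus the post-bronchodilator value. Change is follow-up minus baseline, so a post-bronchodilator baseline adds d to that child's change. The documents give neither the size nor the sign of d.

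Assumed inputs, none from the documents:
- p, the share with no usable Day 1 test: 0.05 to 0.30
- q, the share of those screened post-bronchodilator: 0.25 to 0.50
- d in absolute size: 0.2 to 0.5 LCI units

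Shift in an arm's mean change = p × q × d:
- low: 0.05 × 0.25 × 0.2 = 0.0025
- high: 0.30 × 0.50 × 0.5 = 0.075

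Expected affected children among 50 = 50 × p × q:
- low: 50 × 0.0125 = 0.6
- high: 50 × 0.15 = 7.5

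**Between arms**

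The shift in the between-arm difference is (k1/33 − k0/17) × d, where k1 and k0 are the affected children on LUM/IVA and placebo.
- Equal shares, for example 10% in each arm: (0.10 − 0.10) × d = 0.
- A chance imbalance of 1/33 against 3/17: 0.0303 − 0.1765 = −0.146. In absolute size the difference then moves by 0.146 × 0.2 = 0.029 to 0.146 × 0.5 = 0.073. With a larger assumed d of 1.0 it moves by 0.146.

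**The case against.** The strongest reply is that the plan already handles the usual case. MBW is scheduled on Day 1, before dosing and pre-bronchodilator, and the latest value takes precedence. The section on LCI data blinding (Protocol 10.7.1) names screening and baseline LCI separately, which suggests that Day 1 was the intended baseline. This stands, and it confines the point to a fallback.

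The fallback may also be rare. Children who cannot perform MBW are excluded. Protocol 11.4.2 averages all technically acceptable replicates, and no visible text sets a two-test minimum on Day 1, so a single acceptable replicate may be enough. Nothing in the documents supports a Day 1 failure rate as high as 30%. This stands too; the upper end of the range is an assumption only.

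Text is redacted after the baseline definition in Protocol 12.3.1, in the LCI definition of SAP 9.2.2.2.1, and in the MBW row and derived-variable notes of SAP Appendix A. An LCI-specific baseline rule could be there. That cannot be settled from the public documents.

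A reader might infer that the SAP's condition on the between-arm comparison turns this into a decision error. The documents do not support that. The SAP wording is permissive, either arm can meet the condition, variability is also considered, and Protocol 12.3.3.3 plans the between-arm summary without any such condition. No LCI standard deviation is given, so nothing shows that a shift of this size would move an interval across zero.

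What survives is that the visible rule permits a mismatched baseline, and no visible text flags it or plans a check.

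**Conclusion.** The point holds as a conditional one. Where Day 1 yields no usable MBW and the screening test was post-bronchodilator, that child's LCI2.5 change compares two test conditions.

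Two stronger conclusions might be inferred and should not be. The first is that the LCI endpoint as a whole mixes conditions; it does not, because a valid Day 1 test overrides screening. The second is that the treatment comparison is biased; randomization balances the fallback in expectation, so only chance imbalance remains. The primary MRI analysis is not involved.

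The arm-mean shift of 0.0025 to 0.075 LCI units rests entirely on the assumed p, q and d. Each affected child carries the full assumed 0.2 to 0.5. This is a small matter on one secondary endpoint of an exploratory trial, worth correcting because correction is cheap and conditional on the redacted text not already covering it.

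**What to change.** First check whether the redacted text already sets an LCI-specific baseline rule. If it does not, choose one of two changes:

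1. Perform the screening MBW under the same pre-bronchodilator condition as all later visits, so that any fallback baseline is comparable. The cost is slightly less flexibility at screening.
2. Keep the screening option and state in SAP 9.1 or 9.2.2.2.1 that a pre-bronchodilator, pre-dose MBW is preferred as LCI2.5 baseline. Flag any post-bronchodilator fallback, using the bronchodilator data already collected under Protocol 9.5, and repeat the LCI2.5 summary without those children as a sensitivity analysis. The cost is a sentence or two in the SAP and one extra table.

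Barring post-bronchodilator baselines outright should not be the main remedy. SAP 9.1 does not impute missing data unless specified otherwise, so a child whose only pre-dose test was post-bronchodilator would drop out of the LCI change analysis. In arms of 33 and 17 that exchanges a small shift, balanced in expectation, for missing data.
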